7.5.1.1 Severity

The severity/intensity of AEs will be graded based upon the subject's symptoms according to the current active minor version of the Common Terminology Criteria for Adverse Events (CTCAE, Version 5.0);

http://ctep.cancer.gov/protocolDevelopment/electronic_applications/ctc.htm#ctc_40

AEs that are not defined in the CTCAE should be evaluated for severity/intensity according to the following scale:

- Grade 1 = Mild – transient or mild discomfort; no limitation in activity; no medical intervention/therapy required
- Grade 2 = Moderate – mild to moderate limitation in activity, some assistance may be needed; no or minimal medical intervention/therapy required
- Grade 3 = Severe – marked limitation in activity, some assistance usually required; medical intervention/therapy required, hospitalization is possible
- Grade 4 = Life-threatening – extreme limitation in activity, significant assistance required; significant medical intervention/therapy required, hospitalization or hospice care probable
- Grade 5 = Death - the event results in death

The term “severe” is often used to describe the intensity of a specific event (as in mild, moderate or severe myocardial infarction); the event itself, however, may be of relatively minor medical significance (such as severe headache). This criterion is not the same as “serious” which is based on subject/event outcome or action criteria associated with events that pose a threat to a subject’s life or functioning.

Seriousness, not severity, serves as a guide for defining regulatory obligations.

7.5.1.2 Duration

For both AEs and SAEs, the Investigator will provide a record of the start and stop dates of the event.

7.5.1.3 Action Taken

The Investigator will report the action taken with IP as a result of an AE or SAE, as applicable (e.g., discontinuation, interruption of IP, as appropriate) and report if concomitant and/or additional treatments were given for the event.

7.5.1.4 Outcome

The Investigator will report the outcome of the event for both AEs and SAEs. All SAEs that have not resolved upon discontinuation of the subject’s participation in the study must be followed until recovered (returned to baseline), recovered with sequelae, or death (due to the SAE).

7.5.1.5 Causality

The Investigator must determine the relationship between the administration of IP and the occurrence of an AE/SAE as Not Expected or Expected as defined below:

- Not Expected: A causal relationship of the adverse event to IP administration is **unlikely or remote**, or other medications, therapeutic interventions, or underlying conditions provide a sufficient explanation for the observed event.
- Expected: There is a **reasonable possibility** that the administration of IP caused the adverse event. 'Reasonable possibility' means there is evidence to suggest a causal relationship between the IP and the adverse event.

Causality should be assessed and provided for every AE/SAE based on currently available information. Causality may be reassessed and provided as additional information becomes available.

The Investigator is responsible for assessing the severity of the AE, the causal relationship between any events and the clinical study procedure, activities or device. Additionally, the Investigator is responsible for providing appropriate treatment for the event and for adequately following the event until resolution.

Attribution - the determination of whether an adverse event is related to a medical treatment or procedure.

- Definite - the adverse event is clearly related to the investigational agent(s).
- Probable - the adverse event is likely related to the investigational agent(s).
- Possible - the adverse event may be related to the investigational agent(s).
- Unlikely - The adverse event is doubtfully related to the investigational agent(s).
- Unrelated - The adverse event is clearly NOT related to the investigational agent(s).

8.0 STATISTICAL CONSIDERATIONS

This is an open label, Phase 1b/2 trial to determine the safety/tolerability (phase 1b) and preliminary efficacy (phase 2) of omacetaxine in combination with venetoclax for patients with relapsed/refractory acute myeloid leukemia or myelodysplastic syndrome harboring a *RUNX1* mutation.

Phase 1b: A maximum of 24 patients will be enrolled into this part of the study, with up to 12 patients in each arm (AML or MDS). The dose levels are show in Table 1 and the starting dose is dose level 0.

Dose limiting toxicity (DLT) will be graded according to the NCI Common Terminology Criteria for Adverse Events (CTCAE v5) by organ system. DLTs (see 6.2.1 of the protocol) that occurred within the first 1 cycle after treatment will be used for dose escalation/de-escalation decisions. The Bayesian Optimal Interval (BOIN) design (Liu and Yuan, 2015) will be used to determine the MTD of the combination for each arm. The BOIN design identifies the MTD through minimizing the incorrect decisions of dose escalation and de-escalation (i.e., erroneously escalating/deescalating the dose when the current dose is actually higher/lower than the MTD), thereby optimizing the dose assignment for each enrolled patient. The BOIN design is simple to implement and has been shown to have superior performance through simulations. The BOIN design is algorithm-based, which is similar to the traditional “3+3”; however its overall performance is substantially better.

The following design detail applies to each arm separately. The target toxicity rate for the MTD is $\phi = 0.3$. For each arm, we will enroll and treat patients in cohorts of size 3. To guide dose-escalation decisions, if the observed DLT rate at the current dose is ≤ 0.236 , the next cohort of patients will be treated at the next higher dose level; if it is ≥ 0.359 , the next cohort of patients will be treated at the next lower dose level. These boundaries were created when minimizing decision errors such that $\varphi_1 = 0.18$ is the highest toxicity probability that is considered sub-therapeutic (underdosing) and $\varphi_2 = 0.42$ is the lowest toxicity probability that is deemed overly toxic (overdosing). For the purpose of overdose control, doses j and higher levels will be eliminated from further examination if $\Pr(p_j > 0.3 | \text{data}) > 0.95$, where p_j is the true DLT rate of dose level $j, j = -2, -1, 0, 1$. When the lowest dose is eliminated, stop the trial for safety.

For each arm, the trial design is described through the following three steps:

1. Patients in the first cohort are treated at Dose Level 0.
2. To assign a dose to the next cohort of 3 patients, conduct dose escalation/de-escalation according to the rule displayed in Table 4. When using Table 4, please note the following:
 - a. “Eliminate” means that we eliminate the current and higher doses from the trial to prevent treating any future patients at these doses because they are overly toxic.
 - b. When we eliminate a dose, automatically de-escalate the dose to the next lower level. When the lowest dose is eliminated, stop the trial for safety. In this case, no dose should be selected as the MTD.
 - c. If none of the actions (i.e., escalation, de-escalation or elimination) is triggered, we treat the new patients at the current dose.

- d. If the current dose is the lowest dose and the rule indicates dose de-escalation, treat the new patients at the lowest dose unless the number of DLTs reaches the elimination boundary, at which point terminate the trial for safety.
- e. If the current dose is the highest dose and the rule indicates dose escalation, treat the new patients at the highest dose.

3. Repeat step 2 until the maximum sample size of 12 is reached for a given arm, or stop the arm if the number of patients treated at the current dose reaches 9.

Table 4. Dose escalation/de-escalation rule for the Boin design

	1	2	3	4	5	6	7	8	9
Number of patients treated at current dose	1	2	3	4	5	6	7	8	9
Escalate if # of DLT <=	0	0	0	0	1	1	1	1	2
Deescalate if # of DLT >=	1	1	2	2	2	3	3	3	4
Eliminate if # of DLT >=	NA	NA	3	3	4	4	5	5	5

Note. # of DLT is the number of patients with at least 1 DLT. When none of the actions (i.e., escalate, de-escalate or eliminate) is triggered, stay at the current dose for treating the next cohort of patients. "NA" means that a dose cannot be eliminated before treating 3 patients.

After Phase 1b part of the trial is completed, select the MTD for each arm based on isotonic regression as specified in Liu and Yuan (2015). This computation is implemented by the shiny app "BOIN" available at <http://www.trialdesign.org>. Specifically for each arm, select as the MTD the dose for which the isotonic estimate of the toxicity rate is closest to the target toxicity rate. If there are ties, select the higher dose level when the isotonic estimate is lower than the target toxicity rate and select the lower dose level when the isotonic estimate is greater than or equal to the target toxicity rate. Furthermore, the RP2D will be selected based on safety and efficacy, in Arms A and B independently.

Operation Characteristics

Table 3 shows the operating characteristics of the Boin design based on 1000 simulations using shiny app "BOIN" available at <http://www.trialdesign.org>. The operating characteristics show that the design selects the true MTD, if any, with high probability and allocates more patients to the dose levels with the DLT rate closest to the target of 0.3.

Table 3. Operating characteristics of the Boin design (Dose 0 is the starting dose)

	Dose Level -2	Dose Level -1	Dose Level 0 (starting dose)	Dose Level 1	Number of Patients	% Early Stopping
Scenario 1						
True DLT Rate	0.47	0.55	0.64	0.75		
Selection %	44.2	27.6	8.2	0.1		19.9
% Pts Treated	24.4	36	37.7	1.9	11.8	
Scenario 2						
True DLT Rate	0.11	0.3	0.47	0.67		
Selection %	9.1	52.5	34.3	3.2		0.9
% Pts Treated	5.8	33.8	52	8.4	11.8	
Scenario 3						
True DLT Rate	0.02	0.13	0.3	0.47		
Selection %	0.3	19.3	54.5	25.6		0.3
% Pts Treated	0.4	15.7	58.1	25.9	11.7	
Scenario 4						
True DLT Rate	0.05	0.1	0.15	0.3		
Selection %	0	2.4	26.6	71		0
% Pts Treated	0	3.1	43.8	53.2	11.9	

Phase II:

In phase II portion of the study, patients will be treated at the RP2D level chosen during phase 1b for each arm separately. A maximum of 30 patients will be treated in each arm. For AML patients, the primary efficacy endpoint is overall response, defined as CR, CRh, CRi, PR or marrow clearance of blasts within 3 cycles of treatment. For MDS patients, the primary efficacy endpoint is overall response, defined as CR, PR, HI (Hematologic Improvement), or mCR (marrow clearance of blasts) within 3 cycles of treatment. In addition, we will continue to monitor the DLTs that occurred during the first 3 cycles of treatment.

For each arm, the efficacy and toxicity will be monitored simultaneously using the Bayesian optimal phase 2 (BOP2) design (Zhou, Lee and Yuan, 2017). Specifically, let n denote the interim sample size and N denote the maximum sample size. Let Y_{eff} and Y_{tox} denote the binary efficacy and toxicity endpoints, with $Y_{eff} = 1$ and $Y_{tox} = 1$ indicating that patients experience efficacy and toxicity, respectively. We assume that the joint distribution of (Y_{eff}, Y_{tox}) follows a multinomial distribution with four elementary outcomes: $(Y_{eff}, Y_{tox}) = (1, 1), (1, 0), (0, 1)$ and $(0, 0)$. Let $\mathbf{p} = (P_{11}, P_{10}, P_{01}, P_{00})$ denote the probabilities of observing the four outcomes, and let $p_{eff} = Pr(Y_{eff} = 1)$, $p_{tox} = Pr(Y_{tox} = 1)$ and $p_{efftox} = Pr(Y_{eff} = 1, Y_{tox} = 1)$.

AML Arm:

The treatment is deemed unacceptable if $p_{eff} \leq 0.2$ or $p_{tox} > 0.2$. Thus, we will stop enrolling patients and claim that the treatment is unacceptable if

$$Pr(p_{eff} > 0.2 | data) < \lambda \left(\frac{n}{N} \right)^\alpha,$$

or

$$Pr(p_{tox} \leq 0.2 | data) < \lambda \left(\frac{n}{N} \right)^{\alpha/3},$$

where $\lambda=0.5$ and $\alpha=0.51$ are design parameters optimized to maximize the study power, i.e., probability of correctly concluding an efficacious and safe treatment as acceptable when $p_{eff} = 0.4$, $p_{tox} = 0.1$ and $p_{efftox} = 0.04$, while controlling that the probability of incorrectly claiming an ineffectual and toxic treatment, i.e., type I error, with $p_{eff} = 0.2$, $p_{tox} = 0.2$ and $p_{efftox} = 0.04$, to 10.4%. Note that in the safety stopping rule, the original publication of the design used the probability cutoff $\lambda(n/N)^\alpha$, here the attenuation factor 3 is added (i.e., $\alpha/3$) to obtain stricter interim stopping boundaries to enhance safety.

This optimization is performed assuming a vague Dirichlet prior $Dir(0.04, 0.16, 0.16, 0.64)$ for \mathbf{p} . The prior is chosen such that it corresponds to a prior effective sample size of 1 patient, and the prior estimates of p_{eff} and p_{tox} match the values specified when the treatment is unacceptable. The above decision rule leads to the following optimal stopping boundaries, in cohort size of 6.

Table 4: Optimized stopping boundaries for AML Arm

# patients treated	Stop if # response <=	OR # toxicity >=
6	0	2
12	1	3
18	3	4
24	4	6
30	6	7

When the total number of AML patients reaches the maximum sample size of 30, we conclude that the treatment is acceptable if the number of responses are greater than 6, and the number of toxicities are less than 7; otherwise we conclude that the treatment is unacceptable. The go/no-go criteria in Table 4 are non-binding.

Below are the operating characteristics of the design based on 10000 simulations using the BOP2 web application (BOP2 V1.4.7.0), which is available at <http://www.trialdesign.org>.

Table 5: Operating characteristics for the interim futility and toxicity monitoring in AML Arm

Scenario	Pr(Eff)	Pr(Tox)	Pr(Eff & Tox)	Early Stopping (%)	Claim Acceptable (%)	Average Sample Size
1	0.20	0.20	0.040	85.03	10.44	12.8
2	0.40	0.10	0.040	25.31	73.93	24.8
3	0.40	0.25	0.120	80.66	15.88	13.4
4	0.15	0.30	0.045	98.07	0.77	8.5

MDS Arm:

The treatment is deemed unacceptable if $p_{eff} \leq 0.15$ or $p_{tox} > 0.2$. Thus, we will stop enrolling patients and claim that the treatment is unacceptable if

$$Pr(p_{eff} > 0.15 | data) < \lambda \left(\frac{n}{N} \right)^\alpha,$$

or

$$Pr(p_{tox} \leq 0.2 | data) < \lambda \left(\frac{n}{N} \right)^{\alpha/3},$$

where $\lambda=0.52$ and $\alpha=0.15$ are design parameters optimized to maximize the study power, i.e., probability of correctly concluding an efficacious and safe treatment as acceptable when $p_{eff} = 0.3$, $p_{tox} = 0.1$ and $p_{efftox} = 0.03$, while controlling that the probability of incorrectly claiming an ineffectual and toxic treatment, i.e., type I error, with $p_{eff} = 0.15$, $p_{tox} = 0.2$ and $p_{efftox} = 0.03$, to 9.8%. Note that in the safety stopping rule, the original publication of the design used the probability cutoff $\lambda(n/N)^\alpha$, here the attenuation factor 3 is added (i.e., $\alpha/3$) to obtain stricter interim stopping boundaries to enhance safety.

This optimization is performed assuming a vague Dirichlet prior $Dir(0.03, 0.12, 0.17, 0.68)$ for \mathbf{p} . The prior is chosen such that it corresponds to a prior effective sample size of 1 patient, and the prior estimates of p_{eff} and p_{tox} match the values specified when the treatment is unacceptable. The above decision rule leads to the following optimal stopping boundaries, in cohort size of 6.

Table 6: Optimized stopping boundaries for MDS Arm

# patients treated	Stop if # response \leq	OR # toxicity
		\geq
6	0	2
12	1	3
18	2	4
24	3	5
30	4	7

When the total number of MDS patients reaches the maximum sample size of 30, we conclude that the treatment is acceptable if the number of responses are greater than 4, and the number

of toxicities are less than 7; otherwise we conclude that the treatment is unacceptable. The go/no-go criteria in Table 6 are non-binding.

Below are the operating characteristics of the design based on 10000 simulations using the BOP2 web application (BOP2 V1.4.7.0), which is available at <http://www.trialdesign.org>.

Table 7: Operating characteristics for the interim futility and toxicity monitoring in MDS Arm

Scenario	Pr(Eff)	Pr(Tox)	Pr(Eff & Tox)	Early Stopping (%)	Claim Acceptable (%)	Average Sample Size
1	0.15	0.20	0.030	88.41	9.77	11.5
2	0.30	0.10	0.030	34.21	65.36	23.0
3	0.30	0.25	0.075	86.01	12.85	12.5
4	0.10	0.30	0.030	98.89	0.69	7.8

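### The Phase 1b rule that stops an arm at 9 patients on one dose is not the rule behind the operating characteristics in Section 8.0, and the sentence summarising that table does not match it

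*Combined protocol and SAP*

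**What the plan says.** Section 8.0 specifies a BOIN design for each arm: target DLT rate 0.30, cohorts of 3, at most 12 patients, and a start at dose level 0, the third of four levels. Step 2 assigns each cohort from the BOIN table (the Table 4 headed as the dose escalation/de-escalation rule). Step 2b says that eliminating a dose moves the arm automatically to the next lower level. Step 3 repeats this until 12 patients are reached, "or stop the arm if the number of patients treated at the current dose reaches 9".

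The BOIN table counts patients already treated at the current dose. Its last column, at 9 patients, still contains actions: escalate at 2 or fewer DLTs, de-escalate at 4 or more (the row "Deescalate if # of DLT >="), eliminate at 5 or more. Only 3 DLTs means stay.

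Under Operation Characteristics, "Table 3 shows the operating characteristics of the Boin design based on 1000 simulations". The conclusion drawn from it is of a design that "selects the true MTD, if any, with high probability and allocates more patients to the dose levels with the DLT rate closest"; the benchmark meant is 0.3.

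**The concern.** Read literally, step 3 closes the arm at 9 patients even when the BOIN table says to leave that dose and three places remain. Take the starting dose with 1/3, then 2/6, then 4/9 DLTs. The table says de-escalate, but step 3 ends the arm. No other dose has been tried, so the isotonic rule can only return the dose with an observed 44% DLT rate. With 5/9 the dose is eliminated and the arm ends without an MTD, although levels -1 and -2 are untested; this also conflicts with step 2b. With 2/9 the table says escalate and the arm closes instead.

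If the simulation used a different stopping rule, the printed selection probabilities and sample sizes describe a design other than the one in the text. The selected dose informs the RP2D, which up to 30 patients per arm receive in Phase 2.

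**Working it through.** **Inputs.** Section 8.0 gives target 0.30, limits 0.18 and 0.42, cohorts of 3, start at level 0 and maximum 12. The true DLT rates are those in the operating-characteristics table.

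**Boundaries.** Escalation: ln(0.82/0.70) / ln[(0.30 × 0.82)/(0.18 × 0.70)] = 0.1582/0.6691 = 0.2365. De-escalation: ln(0.70/0.58) / ln[(0.42 × 0.70)/(0.30 × 0.58)] = 0.1881/0.5245 = 0.3585. These agree with the printed 0.236 and 0.359, and every entry of the BOIN table for 1 to 9 patients is reproduced. The decision table is sound; only the stop at 9 is in question.

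**Where the two rules can differ.** To have 9 patients on one dose with places left, the first three cohorts must all be at level 0. That requires 1/3 and then 2/6, so one DLT in each of the first two cohorts. With p the true rate at level 0, the chance of one DLT in a cohort is q = 3p(1 − p)².

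- Written rule: the arm closes at 9 with probability q².
- Conditional rule (stop only if staying): the third cohort must also have exactly one DLT, so the probability is q³.

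Mean N is 12 − 3q² or 12 − 3q³. In scenario 1, elimination of the lowest dose at 9 patients also counts: 0.7045 × 0.5748 × 0.1038 = 0.0420, which removes a further 3 × 0.0420 = 0.126. Elsewhere that term is negligible.

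| Scenario | p | q | q² | q³ | Mean N, written | Mean N, conditional | Printed |
|---|---|---|---|---|---|---|---|
| 1 | 0.64 | 0.2488 | 0.0619 | 0.0154 | 11.69 | 11.83 | 11.8 |
| 2 | 0.47 | 0.3961 | 0.1569 | 0.0621 | 11.53 | 11.81 | 11.8 |
| 3 | 0.30 | 0.4410 | 0.1945 | 0.0858 | 11.42 | 11.74 | 11.7 |
| 4 | 0.15 | 0.3251 | 0.1057 | 0.0344 | 11.68 | 11.90 | 11.9 |

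The conditional rule rounds to the printed value in all four scenarios, the written rule in none. For 1000 runs the standard error under the written rule is 3√[q²(1 − q²)/1000], which is 0.035, 0.038 and 0.029 in scenarios 2 to 4. The printed means lie about 7 to 8 standard errors away, and still about 6 if the printed figures were rounded up as far as possible. With no stop at 9, mean N would be 12.0 in scenarios 2 to 4, so that rule does not fit either.

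**Selection of the true MTD.** This comes from exact enumeration of all paths, with elimination from a Beta(1,1) prior and isotonic regression.

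| Scenario | Written | Conditional | Printed |
|---|---|---|---|
| 2 | 48.3% | 53.4% | 52.5% |
| 3 | 60.1% | 55.2% | 54.5% |
| 4 | 65.2% | 70.3% | 71.0% |

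A chi-square of all printed selection percentages, pooled over the four scenarios, is 6.9 on 11 df (p = 0.80) for the conditional rule and 61.7 on 12 df (p about 1e-8) for the written rule. A stop at 9 except on elimination also fails (46.8 on 11 df, p about 2e-6).

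**How often the written rule overrides the BOIN table.** Multiply q² by the chance that the third cohort has two or three DLTs (leave downward) or none (escalate). Scenario 2: 0.1569 × 0.4551 = 7.1% downward, made up of 5.5% at 4/9, where the dose to be left is selected, and 1.6% at 5/9, where no dose is selected. Upward: 0.1569 × 0.1489 = 2.3%.

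| Scenario | De-escalate or eliminate pending | Escalate pending |
|---|---|---|
| 1 | 4.4% | 0.3% |
| 2 | 7.1% | 2.3% |
| 3 | 4.2% | 6.7% |
| 4 | 0.6% | 6.5% |

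**Summary sentence.** The printed table settles this without simulation. In scenario 2, level 0 (true rate 0.47) receives 52% of patients and the MTD 33.8%; 52 + 8.4 = 60.4% are treated above the MTD. In scenario 1 the level closest to the target receives 24.4%, and level 0 receives 37.7%.

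**The case against.** The strongest reply is textual. Step 3 repeats step 2, and step 2 assigns the next dose. If current dose in step 3 means the dose just assigned, the text is the conditional rule and the printed table is right. But the BOIN table uses the same term for the dose already given, and nothing signals a different meaning in step 3. A dose-finding rule should not depend on that reading.

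The points on size do stand. The rules differ only after 1/3 then 2/6 at the starting dose. The 5.5% in scenario 2 is gross: after 4/9 the conditional rule treats three patients at level -1, and with 0/3 there (0.70³ = 34%) isotonic selection still returns level 0. The net rise in selecting level 0 is from 34.1% to 38.3%, about 4 points. Ending with a downward move pending is not peculiar to the written rule either, since the cap of 12 also causes it: in scenario 2 it happens in 32.9% of arms under the written rule and 29.1% under the conditional one. In scenario 3 the written rule selects the true MTD more often.

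There are safeguards too. The IND Office must approve dose changes, the RP2D also weighs efficacy, and Phase 2 monitors toxicity, though its go/no-go criteria are non-binding. The allocation sentence is a separate matter and adds no weight to the stopping-rule point.

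**Conclusion.** The concern holds. The printed operating characteristics are those of a rule that stops at 9 only when the decision is to stay; step 3 as written does not produce them. Mean N is overstated by 0.1 to 0.3 patients per arm. Against the printed table, true-MTD selection under the written rule is 4.2 points lower in scenario 2, 5.6 higher in scenario 3 and 5.8 lower in scenario 4. In scenario 2 the chance that no dose is selected is 2.6%, against 0.9% printed. This is a moderate inconsistency that should be corrected, and it does not invalidate the design.

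The mean N result rests only on the stated rule and the printed DLT rates. The selection figures also assume variance-weighted isotonic regression with small pseudo-counts (0.05 DLTs, 0.1 patients). The whole argument takes current dose to mean the dose already given, as in the BOIN table. The claim about allocation is contradicted by the printed table whichever rule applies.

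**What to change.** Make step 3, step 2b with the BOIN table, and the operating characteristics agree. There are two ways:

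- add to step 3 that the stop at 9 applies only when the BOIN table's decision is to stay at that dose, which is the rule the printed results match; or
- keep the wording, state that it overrides the BOIN table and step 2b, say what happens when the dose is eliminated at 9, and re-run the simulation.

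In either case, rewrite the summary sentence to say that in scenario 2 most patients are treated above the MTD, and that in scenario 1 the level closest to the target is not the one used most.

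The cost is one phrase or one run of the BOIN app, plus one sentence. The maximum stays at 12 per arm; compared with the literal wording, the first option uses 0.1 to 0.3 more patients per arm on average.

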6.2.1. Definition of Dose-Limiting Toxicity

A dose-limiting toxicity (DLT) is defined as any grade 3 or higher non-hematologic adverse event or abnormal laboratory value occurring during the first cycle on study that cannot be attributed by the investigator to a clearly identifiable cause such as disease progression, underlying illness, concurrent illness, or concomitant medication, with the following exceptions:

- Grade 3 nausea, vomiting or diarrhea that can be managed to < Grade 3 within 7 days with standard antiemetic or antidiarrheal medications
- Grade 3 or 4 electrolyte abnormalities will only be considered DLT if possibly related to study drug, extend beyond 72 hours, and are not corrected by optimal replacement therapy. Venetoclax interruption for up to 72 hours following transient (< 48 hours) chemical changes and laboratory TLS may be allowed and may not be considered a DLT.

Confirmed Hy's law cases will be considered as DLT. A positive Hy's law case is defined as AST or ALT $\geq 3 \times$ ULN in the setting of total bilirubin $\geq 2 \times$ ULN, without findings of cholestasis, and no other reason can be found to explain the combination of increased aminotransferases and total bilirubin, such as viral hepatitis A, B, or C, preexisting or acute liver disease, or another drug capable of causing the observed injury.

Hematologic DLT is defined as Grade ≥ 4 neutropenia and/or thrombocytopenia and no greater than 5% marrow blasts lasting for 6 weeks or more after the start of a course in the absence of underlying MDS. Anemia will not be considered for the definition of DLT.

Patients with neutropenia or thrombocytopenia as a consequence of the disease prior to the start of therapy do not require treatment interruptions for myelosuppression. Dose reductions of the study treatment in these patients may be considered on an individual case basis and discussed with the PI.

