8.4.2. Efficacy Evaluable Population

All patients who complete at least one post-baseline disease status assessment or who discontinue study medication early due to study drug-related toxicity will be considered evaluable for efficacy. Patients who do not meet the aforementioned requirements will be considered non-evaluable for response and may be replaced.

In addition, we will perform a sensitivity analysis for the efficacy endpoint which will include all patients who have received at least one dose of the study treatment (i.e., those who drop off study early due to any reason will be counted as non-responders).

8.4.3. DLT-evaluable population:

Unless doses are missed in Cycle 1 due to DLT(s), a patient must receive at least 70% of the planned doses of venetoclax and omacetaxine to be considered evaluable for DLT. If a patient received fewer doses/days of treatment in the first cycle of treatment for reasons other than a DLT, the patient will be considered non-evaluable for DLT and replaced.

8.5 Analysis Plan:

Descriptive statistics including plots, mean, median and standard deviations will be used to summarize data. For the primary efficacy analysis, we will estimate the ORR for the combination treatment, along with the Bayesian 95% credible interval. The priors for ORR will be (0.2, 0.8) for AML cohort and (0.15, 0.85) for MDS cohort. Event-free survival (EFS) is defined as the time interval between the date of treatment start and the date of [treatment failure, relapse or death from any cause](#). The Kaplan-Meier method will be used to estimate the probabilities of event-free survival (EFS) and overall survival (OS). Log-rank tests will be used to compare among subgroups of patients in terms of EFS or OS. Similar analyses will be performed for the duration of response. MRD negative status and exploratory biomarkers will be summarized graphically and with descriptive statistics. The association between molecular and cellular markers and overall response and/or resistance will be assessed through logistic regression analyses. Paired t-test or Wilcoxon signed rank test will be used to assess the marker change over time. Safety data will be summarized using frequency and percentage, by category and severity.

The Investigator is responsible for completing an efficacy/safety summary report, and submitting it to the IND Office Medical Affairs and Safety Group, for review and approval

- Phase 1b

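### Section 6.2.1 confines non-hematologic DLTs to cycle 1, but the Phase 2 toxicity rule is meant to count DLTs over three cycles

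*Combined protocol and SAP*

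**What the plan says.** Section 6.2.1 holds the only DLT definition in the document. Its non-hematologic part covers "any grade 3 or higher non-hematologic adverse event or abnormal laboratory value occurring during the first cycle on study", with listed exceptions. Its hematologic part is not limited to cycle 1: it concerns grade 4 cytopenia "lasting for 6 weeks or more after the start of a course".

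Section 8.0 refers to 6.2.1 for Phase 1b and then gives its own window: DLTs "that occurred within the first 1 cycle after treatment will be used for dose escalation/de-escalation decisions".

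For Phase 2, Section 8.0 says "we will continue to monitor the DLTs that occurred during the first 3 cycles of treatment". The BOP2 text that follows calls the toxicity endpoint only a binary outcome, so this sentence is the only statement of what is counted. In both arms a toxicity rate above 0.20 is unacceptable. Looks are at 6, 12, 18, 24 and 30 patients, and the boundaries are non-binding.

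Section 8.4.3 also judges DLT evaluability on cycle 1 alone: "If a patient received fewer doses/days of treatment in the first cycle of treatment for reasons other than a DLT", the patient is non-evaluable and is replaced.

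**The concern.** The Phase 2 sentence borrows a term whose definition excludes most of what the sentence asks for. Two teams could follow the document faithfully and enter different numbers into the same stopping rule: one counts all grade 3 or higher non-hematologic events in cycles 1–3, the other only those in cycle 1.

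The direction of the difference is certain. Patient by patient, the count under 6.2.1 can never exceed the three-cycle count. A boundary crossed under the narrow count has therefore been crossed at the same look or earlier under the wide one. The narrow count errs towards continuing treatment and towards a favourable conclusion, which is the wrong direction for a safety rule.

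**Working it through.** **Inputs (Section 8.0, Phase II).** Boundaries as printed, at n = 6/12/18/24/30:

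| Arm | Stop if responses ≤ | Stop if toxicities ≥ |
|---|---|---|
| AML | 0/1/3/4/6 | 2/3/4/6/7 |
| MDS | 0/1/2/3/4 | 2/3/4/5/7 |

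Target response is 0.40 (AML) and 0.30 (MDS). Toxicity cut-off is λ(n/N)^(α/3), with λ = 0.5, α = 0.51 (AML) and λ = 0.52, α = 0.15 (MDS). The stated Dirichlet priors give a Beta(0.2, 0.8) prior for the toxicity rate.

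**Step 1: reproduce the plan.** The formulas give back every printed boundary. Exact multinomial recursion over the five looks gives these chances of claiming acceptability:

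| Arm, scenario (response, toxicity, joint) | Plan | Exact |
|---|---|---|
| AML 0.20, 0.20, 0.04 | 10.44% | 10.25% |
| AML 0.40, 0.10, 0.04 | 73.93% | 74.05% |
| AML 0.40, 0.25, 0.12 | 15.88% | 15.87% |
| MDS 0.15, 0.20, 0.03 | 9.77% | 9.25% |
| MDS 0.30, 0.10, 0.03 | 65.36% | 64.96% |
| MDS 0.30, 0.25, 0.075 | 12.85% | 12.50% |

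The differences are consistent with error from 10,000 simulations. The printed operating characteristics are sound for whatever rate is counted.

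**Step 2: one case at the first look.** Six patients are treated. One has a non-hematologic DLT in cycle 1 and another has a grade 3 non-hematologic event in cycle 2.

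- Three-cycle count, 2 of 6: Pr(p_tox ≤ 0.2) under Beta(2.2, 4.8) is 0.279. The cut-offs are 0.5 × (6/30)^0.17 = 0.380 (AML) and 0.52 × (6/30)^0.05 = 0.480 (MDS). Both arms stop.
- Count under 6.2.1, 1 of 6: under Beta(1.2, 5.8) the probability is 0.658, above both cut-offs. Neither arm stops for toxicity.

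**Step 3: effect on the whole rule.** The documents do not say what share of patients with a DLT would still qualify under 6.2.1 (a cycle-1 event, or a hematologic DLT). I assume 100%, 75% or 50%:

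counted rate = share × true three-cycle rate

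The true three-cycle rates of 0.30 and 0.25 are chosen for illustration. The recursion of step 1 is then run with response at target, response and toxicity independent, and all boundaries followed.

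| True rate | Share counted | Counted rate | Claim acceptable, AML/MDS | Average patients, AML/MDS |
|---|---|---|---|---|
| 0.30 | 100% | 0.30 | 6.7% / 5.0% | 10.8 / 10.3 |
| 0.30 | 75% | 0.30 × 0.75 = 0.225 | 23.4% / 18.5% | 15.0 / 14.0 |
| 0.30 | 50% | 0.30 × 0.50 = 0.15 | 53.4% / 45.3% | 20.9 / 19.3 |
| 0.25 | 100% | 0.25 | 16.2% / 12.5% | 13.4 / 12.5 |
| 0.25 | 75% | 0.25 × 0.75 = 0.1875 | 37.2% / 30.5% | 17.8 / 16.5 |
| 0.25 | 50% | 0.25 × 0.50 = 0.125 | 64.2% / 55.5% | 22.9 / 21.2 |

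Both true rates are above the plan's own limit of 0.20, so every acceptance in this table is a wrong one.

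**The case against.** The best reply is that Section 8.0 sets the window by phase: one cycle for Phase 1b decisions, three for Phase 2. The literal reading of 6.2.1 would leave the Phase 2 sentence nearly empty for non-hematologic events, so three cycles is probably what the authors mean. I accept that as the likely intent. It does not settle the matter, because the definition itself says otherwise, nothing extends it to Phase 2, and 8.4.3 also looks only at cycle 1.

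Three further points stand and limit the weight. The 75% and 50% shares are assumptions. The boundaries are non-binding. Late events are not lost to view: Section 7.5.1 has drug-related events of any grade recorded, and Section 8.5 sends an efficacy and safety summary to the IND Office after every 10 Phase 2 patients per arm, the first once 10 evaluable patients have completed three cycles. What is undefined is the number entered into the formal rule.

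A reader might also infer that the two phases contradict each other on dose. Of the Phase 1b rate the plan says "The target toxicity rate for the MTD is" 0.3, and it will "select as the MTD the dose for which the isotonic estimate of the toxicity rate is closest to the target toxicity rate", while Phase 2 rejects rates above 0.20. Two DLTs in 6 patients means stay in Phase 1b and is the printed stop boundary at n = 6 in Phase 2. The documents do not make this an error. The RP2D is chosen separately from the MTD, on safety and efficacy (Sections 4.2 and 8.0), and Phase 1b dose changes need IND Office approval. The stricter Phase 2 interim boundaries are deliberate. A treatment with a true rate of 0.30 being rejected in about 93% (AML) or 95% (MDS) of trials is the Phase 2 rule working as defined. Nor do all Phase 1b stay results fail in Phase 2: 1 of 3 is also a stay result, and the AML formula would not stop on it (0.384 against a cut-off of 0.338).

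A fixed rule barring such doses as the RP2D would have its own cost. Phase 1b will "stop the arm if the number of patients treated at the current dose reaches 9", so an arm can end with all nine patients at the starting level and no lower level ever treated.

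**Conclusion.** The conflict of windows is real and should be fixed. It concerns wording, but the wording determines the input to a safety stopping rule in both arms. The direction is certain: the literal count stops no earlier and accepts no less often. The size is not known. For a true three-cycle rate of 0.30, wrong acceptance rises from 6.7%/5.0% (AML/MDS) to 23.4%/18.5% or 53.4%/45.3% under assumed counting shares of 75% and 50%. These figures assume the target response, independence of response and toxicity, and boundaries that are followed. They also take the Phase 2 toxicity endpoint to be the DLT named in the sentence before the BOP2 text, which is the natural reading but not a formal definition.

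The finding does not extend to the printed operating characteristics, which reproduce, or to the choice of 0.30 in Phase 1b and 0.20 in Phase 2, which is a design trade-off.

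**What to change.** In Section 6.2.1, replace the words that tie non-hematologic DLTs to cycle 1 with: *during the DLT window (Phase 1b dose decisions: cycle 1; Phase 2 monitoring: cycles 1–3)*.

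The Phase 1b window is already set in Section 8.0, so dose decisions do not change. The BOP2 boundaries and sample size also stay as they are. The cost is one phrase in an amendment and no extra patients.

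Optional, and not a required change: when the RP2D is chosen, the investigators may wish to state how the 0.30 target for the MTD relates to the 0.20 limit in Phase 2.
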